- Information from sleep related examinations in the standard pathway will be manually scored by skilled technicians at each center using predefined criteria. Sleep tests in the SR pathway will be pre-scored by artificial intelligence-based algorithms for characterization of sleep and respiration, and the three PSG in the SR pathway will be manually edited only in epochs identified as unclear by the automated scoring process. For patients with indication for PAP, the titration, training and support will be organized applying local routines at each study center. At PAP-follow up, one night sleep evaluation using the SR self-applied polysomnography procedure will be performed in all patients.

- Evaluation of symptoms and cognitive function with standard care questionnaires and the new European Sleep Questionnaire will be performed together with physical activity assessment at baseline, during treatment and at 3 months follow up.
- Estimated number of patients per center to be randomized: N=42 is the targeted number per site

Study Population:

- Main Inclusion Criteria:
 - Referral to the sleep center due to suspected obstructive sleep apnea as the main question for evaluation
 - Male or female aged 18 years and above
 - \circ $\;$ Willing and able to provide written informed consent $\;$
 - Willing and able to comply with the study design schedule and other requirements
 - (e.g. no long-term travel conflicting with the planned visits throughout the study)
- Main exclusion criteria:
 - o Any ongoing treatment for OSA or Central Sleep Apnea
 - Known significant hypercapnic respiratory failure due to chronic obstructive pulmonary disease or other respiratory condition
 - \circ $\;$ Any other clinically determined contraindication for PAP treatment $\;$
 - o Patients participating in any type of weight loss treatment program
 - Unstable congestive heart failure or angina pectoris
 - Any other condition to the judgement of the investigator which potentially may jeopardize the completion of the study according to protocol
 - History of alcohol or drug abuse during the last year, substance use disorder at screening

Study Duration:

The study started in December 2023 with the first patient inclusion and active patient assessments (last patient out) is expected in July 2025.

Figure 1: SR 001 Study Flow Chart

PSG=polysomnography, PG=polygraphy, SR=Sleep Revolution diagnostic pathway, PAP=Positive Airway Pressure treatment

Trial Design

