All innovation in medicine needs to be justified in terms of cost-benefit. We decided to use stafftime as the primary outcome of the current study. It is estimated that the time of the SR procedure is equal to the time presently used in the SC procedures. Use of the self-applied polysomnography together with machine-learning algorithms of sleep analysis and the digital platform of patient symptom self-reporting will reduce staff time on one hand. On the other hand, user instructions to the patient for the different technologies as well as the evaluation of new information may consume more time compared with the current procedure. We decided to use a non-inferiority study design with 30 minutes as a threshold for equality of staff time within the setting of 24 sleep centers in Europe.

Calculation of the power sample is based on a previous publication (Fischer 2008) and the following assumptions determined from a Delphi round (expert consensus) amongst the participating study centers. More detailed information on staff time for PSG and HSAT currently used at 24 different study sites are not available in the literature. One pilot study for the SR pathway has been performed but no detailed measurement of staff time was performed. However, realistic estimates can be made (see table below).

Work modules	Standard PSG	Standard HSAT	Sleep Revolution	Value
Preparation technical pre/post	15	10	35	
Instructions/Hook up	20-40	5-20	5-30	
Performance of the sleep test	120-480	0 (patient)	0 (patient)	
Evaluation of the sleep test	30-120	5-30	30-90	
Questionnaires	5	5	10	
Additional equipment	0	0	15	
Doctor: interpretation, communication	30-60	15-30	45-60	
Staff time: Estimated range of the mean	220-720	40-95	140-240	
Staff time: Estimated standard deviation of the mean	180	30	60	120

Power calculation:

Significance level (alpha)	1%		
Power (1-beta)	90%	You could say:	
Standard deviation of outcome	120	between the standard and experimental treatment, then 834	
Non-inferiority limit, d	30	sure that the lower limit of a one- sided 99% confidence interval (or equivalently a 98% two-sided	
Sample size required per group	417	confidence interval) will be above the non-inferiority limit of -30.	
Total sample size required	834		
Technical note		Reference	
Calculation based on the formula:		Julious SA. Sample sizes for clinical trials with Normal data. Statis Med. 2004; 23:1921-1986.	

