$n = f(\alpha_s \ \beta) \ \times \ 2 \ \times \ \sigma^2 \ / \ d^2$		How to cite this service	
where σ is the standard deviation, and		Sealed Envelope Ltd. 2012. Power calculator for continuous	
$f(\alpha, \beta) = [\Phi^{-1}(\alpha) + \Phi^{-1}(\beta)]^2$		outcome non-inferiority trial. [Online] Available from: https://www.sealedenvelope.com/power/continuous-noninferior/	
• ¹ is the cumulative distribution function of deviate.	a standardised normal	[Accessed Thu Jan 19 2023].	

The power calculation suggests 417 patients in each group, the expected drop-out rate of patients is 20% (results from the SR pilot study, Ferretti et al 2024), resulting in 500 patients per group.

7. Randomization and Blinding

Randomization Method

At screening, the order of diagnostic tests will be randomized. The "randomization system" (RS) will assign an unique identification number to the patient known as the patient number. This number will be associated with the patient throughout the study. Each patient signing an informed consent form (ICF) must be entered into the RS regardless of eligibility to obtain a patient number. This 8-digit number will consist of a 3-digit country specific code, followed by a 2-digit site identification and a 3-digit number assigned sequentially within each site to each patient, starting at 001.

At the randomization visit, all eligible patients will be randomly assigned in a 1:1 ratio to follow the routine clinical management or to be part of the SR clinical pathway. Centres using polysomnography as routine sleep evaluation procedure are asked to use this method in all of the study patients at this centre, and vice versa for those centers using cardiorespiratory polygraphy as the routine method. By this procedure, the study aims to recruit at least 40% of patients in the traditional clinical routine to be assessed by PSG. No formal stratification for anthropometric factors like age, BMI, gender or comorbidities will be performed.

Patients will be assigned a randomization number through the RS. Once a randomization number is allocated to one patient, it may not be assigned to another patient even if the former discontinued the study. The randomisation list is exemplified in appendix B.

Blinding

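### SAP section 6: 500 patients per group does not fully cover the expected 20% drop-out; 400 would remain against the 417 required, a small shortfall

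*SAP*

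**What the plan says.** Section 6 (Sample Size Calculation) gives these inputs for the primary non-inferiority comparison of staff time:

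- a one-sided alpha of 1%, described as a one-"sided 99% confidence interval (or equivalently a 98% two-sided" interval;
- "Power (1-beta) 90" per cent;
- "Standard deviation of outcome 120" (minutes);
- a margin of 30 minutes: "non-inferiority study design with 30 minutes as a threshold for equality of staff time";
- no true difference: "It is estimated that the time of the SR procedure is equal to the time presently used in the SC procedures".

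The result is 417 per group, 834 in total. The section then allows for attrition: "The power calculation suggests 417 patients in each group, the expected drop-out rate of patients is 20" per cent, a rate taken from the project's pilot study, "resulting in 500 patients per group". It does not show how 417 became 500.

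Section 3 (Study Design) sets recruitment by centre: "N=42 is the targeted number per site", with 24 sites.

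**The concern.** One sentence holds three figures that do not fit together: 417 needed, 20% lost, 500 randomised. An allowance for drop-out should leave the required number after the loss. This one leaves 400.

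The figure 500 is what one gets by adding 20% to 417. Dividing 417 by the 80% expected to remain gives more. The multiplier is an inference, since no formula is printed, but the point does not depend on it: 80% of 500 is below 417 however 500 was reached.

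At stake is the justification of the sample size for the primary endpoint. If the 20% refers to patients without a staff-time value, the sample size and the 90% power in section 6 cannot both stand.

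**Working it through.** **Inputs.** From section 6: one-sided alpha 1% (z = 2.326), power 90% (z = 1.282), SD σ = 120, margin d = 30, true difference 0, drop-out 20%. From section 7: 1:1 allocation. From section 3: 24 sites with 42 patients each.

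**Step 1: reproduce the plan's 417.** The SAP's formula is n = f(α, β) × 2 × σ² / d², with f = (2.326 + 1.282)² = 13.017.

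n = 13.017 × 2 × 120² / 30² = 416.5, rounded up to 417 per group. This agrees with the SAP.

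**Step 2: the drop-out allowance.**

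- Needed to keep 417 after 20% loss: 417 / (1 − 0.20) = 521.25, so 522 per group (1,044 in total).
- Simple mark-up: 417 × 1.2 = 500.4, which matches the stated 500.
- Remaining from 500: 500 × 0.80 = 400, which is 417 − 400 = 17 short (4.1% of 417).
- Remaining from the site target: 24 × 42 = 1,008, or 504 per group; 504 × 0.80 = 403.2, still below 417.

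**Step 3: power at the remaining number.** Power = Φ(d / SE − z), with SE = σ√(2/n).

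For n = 400: SE = 120 × √(2/400) = 8.485; 30/8.485 = 3.536; 3.536 − 2.326 = 1.209; Φ(1.209) = 0.887.

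| Patients per group with data | One-sided alpha | Power |
|---|---|---|
| 417 (required) | 1% | 90.0% |
| 400 (500 less 20%) | 1% | 88.7% |
| 403 (504 less 20%) | 1% | 88.9% |
| 500 (no loss of staff-time data) | 1% | 94.8% |
| 400 | 2.5% | 94.2% |

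**Step 4: the loss that 500 can absorb.** 1 − 417/500 = 0.166. With 500 per group, 90% power at one-sided 1% holds as long as no more than 16.6% lack staff-time data.

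**The case against.** A reader might infer from the mismatch that the trial is underpowered, or that the 90% is simply not achieved. The SAP does not support a statement that strong, for four reasons.

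- **The gap is small against its inputs.** It is 1.3 points at 400 per group and 1.1 at the site target. The SD of 120 is an expert-consensus value set beside component SDs of 30, 60 and 180. At 400 per group, 90% is restored if σ = √(400 × 30² / (2 × 13.017)) = 117.6, about 2% smaller. This stands.
- **Not every drop-out need lack the primary outcome.** Section 8.4 measures staff time from V1a to V1c for the randomised procedure, which is the one done first. A patient lost during the second pathway or the PAP follow-up can still have that value, and the primary analysis includes all randomised patients. The SAP does not say which phase the 20% covers. This stands, and it makes 88.7% conditional. It does not rescue the sentence: section 6 itself treats the 20% as reducing the usable number, and an intention-to-treat set does not supply staff time for someone who left before it was recorded. The optional imputation in section 8.10 would not by itself recover lost information. The per-protocol analysis of staff time also includes only patients who completed the diagnostic pathway.
- **Section 8.4 reports a 95% interval.** Read as the non-inferiority test, this is one-sided 2.5%, and 400 per group gives 94.2%. The figure is correct, but section 6 claims 90% power at one-sided 1%, so a different alpha does not make that claim consistent. The disagreement between the two sections is a separate matter; here it means that any power figure must carry its alpha.
- **No decision changes.** The SAP is signed in May and June 2025 and last patient out is expected in July 2025. This supports correcting the text only.

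**Conclusion.** The point holds as a minor arithmetic inconsistency. On section 6's own inputs, 500 per group does not cover 20% drop-out: 400 remain (403 from the site target) against 417 required, and 522 would be needed.

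The consequence is a planned power of about 88.7% (88.9% with 403) instead of 90%. This rests on SD 120, margin 30, true difference 0, one-sided alpha 1%, and all drop-outs lacking staff-time data. If 16.6% or fewer lack it, the 90% stands. If all 500 per group contribute, power is 94.8%.

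The documents do not show that the trial is materially underpowered. The margin, the model and the interpretation of the primary result are unaffected.

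**What to change.** Replace the last sentence of section 6 with a conditional statement, and do not enrol more patients. Suggested wording:

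*500 per group allows for up to 16.6% of patients without staff-time data at 90% power (one-sided alpha 1%, SD 120, margin 30). If the full 20% lack staff-time data, 400 per group remain and power is about 88.7%.*

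It would help to add which study phase the 20% refers to, so that readers can see which part of the statement applies.

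The cost is one or two sentences in section 6 and a slightly less favourable power figure. No endpoint, population, model or procedure changes.

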8.1. General Considerations

The primary study outcome variable (staff time) will be analysed using an intent-to-treat (ITT) as well as a per-protocol analysis. Similarly, secondary and tertiary/exploratory outcome variables will be performed in the per protocol analysis cohort.

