- Secondary objective: To evaluate novel Sleep Revolution diagnostic variables and their relation to symptom burden, patient 's help request during baseline assessment and outcome of sleep apnea treatment with CPAP after 3 months.
- Further secondary objectives: Feasibility and safety of the self-applied sleep testing and the digital platform for both sleep and symptom assessment

Study Design:

The study is performed at 24 sites of the European Sleep Apnea Database (ESADA) network in 15 European countries. Most relevant details of the study design are listed below:

- Study SR-001 is a multi-center, 2-arm, cross-over study comparing the diagnostic impact and accuracy of two different diagnostic pathways on the outcome of diagnosis and CPAP treatment in patients with suspected OSA. Patients referred to one of 24 sleep centers of the ESADA network participating in the Sleep Revolution project will be studied using both the clinical routine of OSA evaluation (standard care) and the novel Sleep Revolution based diagnostic pathway including self-applied polysomnography over three nights, digitally based symptom evaluation, and actigraphy based assessment of sleep wake rhythm and physical activity (experimental condition). Study participants will be randomized with respect to the order of two diagnostic pathways. The decision on diagnosis and treatment will be based on information from the first diagnostic procedure (SC or SR), the results from the second pathway will be blinded both to the investigator (sleep specialist) and the patient.
- Following diagnostic steps including sleep testing, symptom assessment and evaluation of physical status evaluation, patients will receive information regarding the sleep disorder diagnosis by the sleep specialist. In case of a diagnosis of clinically relevant OSA, treatment recommendations will be provided. Only patients initiating therapy with PAP will be approached for participation in the subsequent part of the study- treatment start and follow up for 3 months.

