- Self-applied polysomnography is technically feasible but successful application of the technique depends on active patient involvement/participation with acceptable technical failure rates below 10% of sleep tests.
- The first night effect in multiple sleep recordings on sleep apnea metrics is limited and does not systematically differ from the night to night variability between night 2 and 3.
- The outcome of PAP treatment is non-inferior in the SR pathway to SC pathway.
- Additional secondary analyses and hypotheses may be defined including separate protocols and SAP´s. Those will be reviewed and need to be approved by the SR executive committee. More details including an updated SAP will be made available.

6. Sample Size Calculation

Staff time is an important factor for the clinical feasibility of a diagnostic pathway. Today's clinical standard of sleep apnea diagnosis varies considerably between centers and countries in Europe (Fietze 2022). In house polysomnography as well as HSAT are frequently used to establish the final OSA diagnosis and resources in staff-time varies considerable between these two diagnostic methods.

The novel SR pathway aims to provide more diagnostic accuracy by means of three nights of gold standard sleep analysis at patient's home compared to the single-night measures in the sleep laboratory used today. In addition, the SR pathway provides significant enhancement of clinical

phenotyping of patient symptoms, complaints, primary request of help as well as detailed information about relevant aspects of lifestyle and personal habits (physical activity, alcohol consumption, sleep hygiene) and neurocognitive function. The gain of knowledge about the patient ´s disease burden is obvious when using such a comprehensive approach. However, the actual cost in terms of staff time has not yet been evaluated.

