8.3 Analysis Populations

• Enrolled Population

The enrolled population will include all individuals who sign the informed consent.

• Intent-to-Treat Population (ITT)

The ITT population will include all patients who are randomized, irrespective of any deviation from the protocol or premature discontinuation. The group assignment will be designated according to initial randomization. The ITT population will serve to enable an analysis of the primary outcome variable (staff time).

• Per protocol analysis population (PPAP) for the primary outcome

All patients finally fulfilling the complete diagnostic pathway (SR och traditional) will constitute the per protocol analysis population for secondary and tertiary outcome analyses.

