8.5. Secondary Analysis

A number of secondary analyses are listed in chapter 4 and in appendix C, secondary, tertiary and exploratory endpoints. A detailed description of all these analyses to be performed in the upcoming years is not feasible for this SAP. Therefore, only a few most important analyses are described below exemplifying the advanced statistical models to be applied to the large amount of study data.

• Example 1: Association between Overnight Hypoxic Burden and Change in ESS Score

This section describes the analysis plan for evaluating the association between overnight hypoxic burden and the change in ESS score after 3 months of CPAP treatment in the Sleep Revolution study arm, compared to the association between AHI (single night assessment) and ESS change in the conventional management arm. Both models will be adjusted for confounders of ESS change like age, sex, BMI, AHI and ESS score at baseline.

Analysis Population: The primary analysis will be conducted on the intention-to-treat (ITT) population, including all randomized patients according to their assigned group.

Descriptive Statistics: Descriptive statistics will be presented for the primary outcome by group, including: Mean, standard deviation, Median, interquartile range and Minimum/Maximum

Primary Analysis: To evaluate the association between overnight hypoxic burden and change in ESS score, and compare it with the association between AHI and ESS change, two linear mixed-effects models (LMM) will be used:

1. Sleep Revolution Study Arm:

- Fixed effects: Overnight hypoxic burden, age, sex, BMI, baseline AHI and ESS. We will analyse the collinearity between AHI and hypoxic burden metrics. If the collinearity is very high we need to decide to use AHI or HB or we will perform an analysis by tertiles of AHI.

- Random effect: Center

2. Conventional Management Arm:

- Fixed effects: AHI, age, sex, BMI, baseline AHI and ESS

- Random effect: Center

Model specification for the Sleep Revolution and standard care study arm, respectively: ESS_Change_ij = $\beta 0 + \beta 1 *$ HypoxicBurden_ij + $\beta 2 *$ Age_ij + $\beta 3 *$ BMI_ij + $\beta 4 *$ SEX_ij + $\beta 5 *$ BaselineAHI_ij + $\beta 6 *$ BaselineESS_ij + u_j + ϵ_i j where:

- ESS_Change_ij is the change in ESS score for patient i in center j
- β 0 is the intercept
- β 1- β 6 are the fixed effect coefficients
- u_j ~ N(0, σ_u^2) is the random effect for center
- $\varepsilon_{ij} \sim N(0, \sigma^2)$ is the residual error

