All reported AEs will be listed and compared in the two study groups. The incidence of PAP treatment-emergent AEs will be included in incidence tables. Events with missing onset dates will be included as treatment emergent. If a patient experiences more than 1 occurrence of the same AE, the occurrence with the greatest severity and the closest association with the study treatment will be used in the summary tables. SAEs and AEs causing discontinuation will be tabulated. All AEs will be listed by patient, along with information regarding onset, duration, relationship and severity to study treatment, action taken with study treatment, treatment of event, and outcome.

- Vital signs like blood pressure and heart rate will be summarized using descriptive statistics, including mean values and mean change from baseline values, as well as numbers of patients with values outside limits of the normal range at each time point.
- Summary tables will be provided for concomitant medications initiated during the study period.

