8.6. Exploratory Analysis

Drop out analysis: Factors predicting loss of data in the SR care pathway (sleep test, SR App, ESQ)

Results from bio-sample analysis (baseline, treatment response)

- \circ $\;$ Feasibility and rate of completeness using three nights SAS procedure $\;$
- Patient reported tolerability of the SAS procedure

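### The default population for secondary and exploratory outcomes is pathway completers, which does not suit outcomes that count failure or loss and conflicts with other parts of the SAP

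*SAP*

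**What the plan says.** Section 8.1 has the primary outcome analysed by ITT and per protocol, then adds: "Similarly, secondary and tertiary/exploratory outcome variables will be performed in the per protocol analysis cohort". Section 8.3 defines the cohort: "All patients finally fulfilling the complete diagnostic pathway (SR och traditional) will constitute the per protocol analysis population for secondary and tertiary outcome analyses". I read the Swedish conjunction as 'and', so both pathways are required. The bullet's own title refers to the primary outcome, while its sentence refers to secondary and tertiary outcomes. For ITT, section 8.3 names one use: "The ITT population will serve to enable an analysis of the primary outcome variable (staff time").

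The outcomes that fall under this default include:

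- Section 3, Study Objective: "Further secondary objectives: Feasibility and safety of the self-applied sleep testing and the digital platform for both sleep and symptom assessment".
- Section 4: the number of acceptable SR recordings over one, two or three nights, completeness of app and ESQ data, data-transfer failure, and (as exploratory) the technical failure rate of each pathway.
- Section 5, secondary hypotheses: "acceptable technical failure rates below 10% of sleep tests".
- Section 8.6: "Drop out analysis: Factors predicting loss of data in the SR care pathway (sleep test, SR App, ESQ").

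Section 8.5 departs from the default. Example 1 states: "Analysis Population: The primary analysis will be conducted on the intention-to-treat (ITT) population, including all randomized patients according to their assigned group", with per protocol as a sensitivity analysis, and Example 2 follows the same principle. Example 3 (safety) states "All reported AEs will be listed and compared in the two study groups" and plans a table of AEs causing discontinuation. It names no analysis population.

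**The concern.** A failure rate, a completeness rate or a drop-out analysis describes what happens to everyone who sets out on a procedure. If the analysis set is limited to those who reached the end, patients who gave up because the device, the app or the data transfer failed are taken out of both numerator and denominator. The drop-out analysis then loses the patients who dropped out.

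Feasibility and safety of self-applied testing are stated secondary objectives, and one hypothesis has a numerical limit, so the choice of population can affect whether that hypothesis is judged to be met. Because 8.1 and 8.3 say one thing and 8.5 another, the analyst would have to choose a population after the data are in.

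Two smaller problems follow from the same definitions. First, section 8.4 defines the primary outcome as staff time for the randomised procedure only, yet the per-protocol set requires both pathways. The per-protocol check of staff time therefore drops patients for not completing a second pathway that does not enter the outcome. Second, every patient is due to undergo both procedures, so a comparison of diagnostic-phase AEs by randomised group contrasts the order of the procedures, not SR with SC.

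**Working it through.** **The plan's own figures.** Section 6 uses a one-sided alpha of 1%, power 90%, SD 120 and margin 30: n = (2.326 + 1.282)² × 2 × 120² / 30² = 13.02 × 32 = 416.6, that is 417 per group, as stated. The expected drop-out of 20% is then added: 417 × 1.2 = 500.4, stated as 500 per group or 1000 in all. Only the 20% is used below; whether this is the right way to inflate is a separate matter.

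**Patients outside the cohort.** If the 20% were all failures to complete both diagnostic pathways, 1000 × 0.20 = 200 would be outside and 800 inside. The SAP does not say at what stage the drop-out is expected, so 5% is shown as a second case.

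**Formula.** With d the share outside the cohort, f_c the failure rate in completers and f_n the rate in non-completers:

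overall rate = (1 − d) × f_c + d × f_n

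The rates f_c and f_n are assumptions, because the SAP gives neither. Take f_c = 8%, a value that would satisfy the 10% limit if only completers were analysed.

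| f_n | d = 20% | d = 5% |
|---|---|---|
| 8% (no relation to completion) | 6.4 + 1.6 = 8.0% | 7.6 + 0.4 = 8.0% |
| 10% | 6.4 + 2.0 = 8.4% | 7.6 + 0.5 = 8.1% |
| 100% | 6.4 + 20.0 = 26.4% | 7.6 + 5.0 = 12.6% |

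At d = 20%, intermediate values of f_n of 25% and 50% give 11.4% and 16.4%.

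**Where the 10% limit is crossed.** Solve (1 − d) × 8% + d × f_n = 10%. At d = 20%, f_n = (10 − 6.4)/0.20 = 18%. At d = 5%, f_n = (10 − 7.6)/0.05 = 48%.

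**Unit.** The hypothesis counts sleep tests and the table weights by patients. The two agree if each patient counts for the same number of scheduled tests. If only attempted tests count and non-completers attempted fewer, their weight is smaller than d and the shift is smaller.

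**Populations side by side.**

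| Outcome | Under 8.1/8.3 | Elsewhere in the SAP |
|---|---|---|
| Technical failure, completeness | completers | no other population named |
| Drop-out analysis | completers | no other population named |
| Examples 1 and 2 | completers | ITT (8.5) |
| AEs | completers | all reported AEs, population not named (8.5) |
| Staff time, per-protocol check | both pathways completed | outcome covers the randomised pathway only (8.4) |

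**The case against.** The strongest reply is that the SAP does not apply the default throughout. Examples 1 and 2 are set in ITT, so it would be wrong to infer that every secondary analysis is confined to completers. What the text shows is an unsuitable default together with a contradiction.

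A reader might also infer that AEs in patients who stopped would go uncounted. The documents do not support that. Example 3 lists all reported AEs and tabulates those causing discontinuation; what is missing is the denominator. Nor are discontinuations during PAP treatment removed, because the cohort is defined by the diagnostic pathway alone.

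A further tempting reading is that the below-10% hypothesis would be met by construction. That does not follow either. Completing the pathway is not defined, and section 4 counts patients with one, two or three acceptable nights, so some failed nights may stay in the set. If failure is unrelated to completion, there is no bias at all. Loss of app or ESQ data can also occur in pathway completers, so the drop-out analysis would be truncated but not empty. Section 8.2 promises numbers evaluable and the rate of missing data, but names no population for them.

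On safety by randomised group, the criticism is limited to the diagnostic phase. Randomisation decides which pathway guides the clinical decision, so for PAP-phase AEs the group comparison remains meaningful.

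All of this stands and limits the point. It does not remove it: for technical failure, completeness and drop-out, the only population the SAP assigns is the completer cohort.

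**Conclusion.** The point holds in limited form. Followed as written, sections 8.1 and 8.3 condition the technical failure rate, the below-10% hypothesis, completeness and the drop-out analysis on completing the diagnostic pathway. The likely direction is a failure rate that is too low. Its size cannot be known from the SAP: under the assumed rates, the understatement runs from nothing, through 0.4 percentage points, to 18.4 points (26.4 − 8.0) with 20% outside the cohort, and reaches 4.6 points at most (12.6 − 8.0) with 5% outside.

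The populations for Examples 1 and 2 are contradictory and the safety denominator is unresolved. The per-protocol staff-time check carries an unnecessary condition, but the primary ITT analysis and the sample size are not affected.

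**What to change.** In 8.1 and 8.3, replace the single default with a population for each endpoint family:

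- **Technical failure and completeness:** all patients issued the SR equipment, counted per sleep test for the 10% hypothesis. Report withdrawal before issue separately, so that it is not mixed with technical failure.
- **Drop-out analysis:** all randomised patients.
- **Safety:** everyone who began any study procedure. Tabulate diagnostic-phase AEs by the procedure under way at onset, and PAP-phase AEs by randomised group.
- **Per-protocol check of staff time:** completion of the randomised first pathway only.
- **Within-patient comparison of sleep tests:** keep completers of both pathways.

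Then reconcile 8.1 and 8.3 with the ITT statement in 8.5.

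The cost is SAP wording and one derived flag for the AE period. The sample size does not change. The downside is that reported failure rates may be less favourable.
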